## **Assessment of AE Outcome**

The investigator will assess the outcome of all unsolicited AEs (including SAEs) recorded during the study, as:

- Resolved
- Resolving
- Not resolved
- Resolved with sequelae
- Fatal (for SAEs only)

#### Follow-up of AE and SAE

- If information is not available at the time of the first report becomes available at a later date, the investigator should complete a follow-up SAE form or provide other written documentation and submit it to the monitor/Pharmacovigilance immediately within 24 hours of receipt.
- All SAEs will be followed up until satisfactory resolution or until the Investigator deems the event to be chronic or the patient to be stable.

### 11.3.5 Reporting of SAEs, and Other Reportable Safety Events to the Medical monitor

- Any event considered to be serious should be recorded on the SAE reporting form. All SAEs, regardless of relationship, and pregnancies must be reported via eCRF within 24 hours of the Investigator becoming aware of the event. Other supporting documentation may be requested by the Sponsor and should be provided as soon as possible.
- The primary mechanism for reporting an SAE to the medical monitor and pharmacovigilance will be the electronic data collection tool.
  - o If the electronic system is unavailable, then the site will use the paper SAE form in order to report the event within 24 hours.
  - The site will enter the SAE data into the electronic system as soon as it becomes available.
- After the study is completed at a given site, the electronic data collection tool will be taken off-line to prevent the entry of new data or changes to existing data.
- If a site receives a report of a new SAE from a study participant or receives updated data on a previously reported SAE after the electronic data collection tool has been taken off-line, then the site can report this information on a paper SAE form or to the Medical Monitor by phone. Contacts for SAE reporting can be found in the Investigator site file.
- Following notification from the Investigator, Sponsor's Monitor (or designee) will report events that are serious, unexpected and are considered to be causally related to the study products (SUSARs) to the competent authorities (CA) within the required timelines: fatal and life-threatening events within 7 calendar days and all other SAEs within 15 calendar days.
- The Investigator (or designee) will be responsible for reporting the SUSAR to ethics committees.

### 11.4 Appendix 4: Contraceptive guidance and collection of pregnancy information

#### 11.4.1 Definitions

### Woman of childbearing potential (WOCBP)

A woman is considered fertile following menarche and until becoming postmenopausal unless permanently sterile (see below).

If fertility is unclear (e.g., amenorrhea in adolescents or athletes) and a menstrual cycle cannot be confirmed before first dose of study intervention, additional evaluation should be considered.

Women in the following categories are not considered WOCBP

- Premenarchal
- Premenopausal female with 1 of the following
  - o Documented hysterectomy,
  - o Documented bilateral salpingectomy,
  - o Documented bilateral oophorectomy,

For individuals with permanent infertility due to an alternate medical cause other than the above (e.g., Mullerian agenesis, androgen insensitivity), Investigator discretion should be applied to determining study entry.

Note: Documentation can come from the site personnel's: review of the participant's medical records, medical examination, or medical history interview.

Postmenopausal female

A postmenopausal state is defined as no menses for 12 months without an alternative medical cause.

A high follicle-stimulating hormone (FSH) level in the postmenopausal range may be used to confirm a postmenopausal state in women not using hormonal contraception or hormonal replacement therapy (HRT). However, in the absence of 12 months of amenorrhea, confirmation with more than one FSH measurement (>ULN as defined by central laboratory readout) is required.

Females on HRT and whose menopausal status is in doubt will be required to use one of the non-estrogen hormonal highly effective contraception methods if they wish to continue their HRT during the study. Otherwise, they must discontinue HRT to allow confirmation of postmenopausal status before study randomization.

#### 11.4.2 Contraceptive guidance

Mandatory use of contraception must cover the study drug administration period plus 5 times the half-life of liraglutide (half-life around 13 hours) i.e. 5 days (in order to cover extreme values). Contraceptives allowed during the study includea:

## Highly Effective Methodsb That Have Low User Dependency

- Implantable progestogen-only hormone contraception associated with inhibition of ovulationc
- Intrauterine device (IUD)
- Intrauterine hormone-releasing system (IUS)c
- Bilateral tubal occlusion
- Vasectomized partner

(Vasectomized partner is a highly effective contraceptive method provided that the partner is the sole sexual partner of the woman of childbearing potential and the absence of sperm has been confirmed. If not, an additional highly effective method of contraception should be used. (Spermatogenesis cycle is approximately 90 days.)

## Highly Effective Methodsb That Are User Dependent

• Combined (estrogen- and progestogen-containing) hormonal contraception associated with inhibition of ovulation

- oral
- intravaginal
- transdermal
- injectable
- Progestogen-only hormone contraception associated with inhibition of ovulation
  - oral
  - injectable
- Sexual abstinence

(Sexual abstinence is considered a highly effective method only if defined as refraining from heterosexual intercourse during the entire period of risk associated with the study intervention. The reliability of sexual abstinence needs to be evaluated in relation to the duration of the study and the preferred and usual lifestyle of the participant.)

- a Contraceptive use by men or women should be consistent with local regulations regarding the use of contraceptive methods for those participating in clinical studies.
- b Failure rate of <1% per year when used consistently and correctly. Typical use failure rates differ from those when used consistently and correctly.
- c If locally required, in accordance with Clinical Trial Facilitation Group (CTFG) guidelines, acceptable contraceptive methods are limited to those which inhibit ovulation as the primary mode of action.

Note: Periodic abstinence (calendar, symptothermal, post-ovulation methods), withdrawal [coitus interruptus]), spermicides only, and lactational amenorrhea method (LAM) are not acceptable methods of contraception for this study. Male condom and female condom should not be used together (due to risk of failure with friction).

### 11.4.3 Collection of pregnancy information

### Male participants with partners who become pregnant

- The Investigator will attempt to collect pregnancy information on any male participant's female partner who becomes pregnant while the male participant is in this study. This applies only to male participants who receive the investigational medicinal product.
- After obtaining the necessary signed informed consent from the pregnant female partner directly, the Investigator will record pregnancy information on the appropriate form and submit it to the Sponsor within 24 hours of learning of the partner's pregnancy. The female partner will also be followed to determine the outcome of the pregnancy.
- Information on the status of the mother and child will be forwarded to the Sponsor. Generally, the follow-up will be no longer than 6 to 8 weeks following the estimated delivery date. Any termination of the pregnancy will be reported regardless of fetal status (presence or absence of anomalies) or indication for the procedure.
- The Investigator should assess if there was any relationship between the outcome and the exposure to study drug.

### Female participants who become pregnant

- The Investigator will collect pregnancy information on any female participant who becomes pregnant while participating in this study. The initial information will be recorded on the appropriate form and submitted to the Sponsor within 24 hours of learning of a participant's pregnancy.
- The participant will be followed to determine the outcome of the pregnancy (i.e., healthy birth, spontaneous or voluntary abortion, presence or absence of any birth defects, congenital abnormality, or complications for the mother and/or newborn). The Investigator will collect follow-up information on the participant and the neonate, and the information will be forwarded to the Sponsor. Generally, follow-up will not be required for longer than 6 to 8 weeks beyond the estimated delivery date. Any termination of pregnancy will be reported, regardless of fetal status (presence or absence of anomalies) or indication for the procedure.
- Any pregnancy complication or elective termination of a pregnancy for medical reasons will be reported as an AE or SAE.
- A spontaneous abortion (occurring at <22 weeks gestational age) or still birth (occurring at >22 weeks gestational age) is always considered to be an SAE and will be reported as such.
- Any post-study pregnancy related SAE considered reasonably related to the study intervention by the Investigator will be reported to the Sponsor as described in Section 8.3.4. While the Investigator is not obligated to actively seek this information in former study participants, he or she may learn of an SAE through spontaneous reporting.
- Any female participant who becomes pregnant while participating in the study will discontinue study intervention or be withdrawn from the study.
- The Investigator should assess if there was any relationship between the outcome and the exposure to study drug.

### 11.5 Appendix 5: Exploratory tests

Exploratory tests will be described in a separate document.

## 11.6 Appendix 6: Abbreviations

ADAMTS: a disintegrin and metalloproteinase with thrombospondin motifs

AE: adverse event

AESI: adverse event of special interest

ALT: alanine aminotransferase AST: aspartate aminotransferase

ATC: anatomical therapeutic chemical

AUC: area under the curve CA: competent authority

CFR: Code of Federal Regulations

CIOMS: Council for International Organizations of Medical Sciences

CrCl: creatinine clearance
Cmax: maximum concentration

CNS: central nervous system

CONSORT: consolidated standards of reporting trials

COVID-19: coronavirus infectious disease due to SARS-CoV-2

CREB: cAMP response element binding protein

CRF: case report form CSR: clinical study report

CTC AE: common terminology for adverse events

DDD: defined daily dose

DMM: destabilization of the medial meniscus DMOAD; disease-modifying osteoarthritis drug

DMP: Data management plan

DSMB: data and safety monitoring board

EC: ethics committee ECG: electrocardiogram

eCRF: electronic case report form EMA: european medical agency

EoS: End of Study
EoT: End of Treatment

FDA: food and drug administration

FIM: first-in-man

GCP: Good Clinical Practice

GDPR: General Data Protection Regulation

GLP: good laboratory practice

GLP-1(R): glucagon-like peptide 1 (receptor)

HBsAg: hepatitis B surface antigen HCG: human chorionic gonadotropin HCV-Ab: hepatitis C virus antibody

HED: human equivalent dose

HIV: human immunodeficiency virus hMSC: human mesenchymal stem cells

HPLC: high performance liquid chromatography

HRT: hormonal replacement therapy

IB: investigator's brochure ICF: informed consent form

ICH: international council for harmonisation

IA: intra-articular

IC50: half maximal inhibitory concentration

IEC: Independent Ethics Committee

Ig: immunoglobulin IL-6: interleukin 6

IMP: investigational medicinal product

IV: intravenous(ly)

KL: Kellgren and Lawrence classification

MABEL: minimum anticipated biological effect level

MIA: mono-iodo-acetate

MedDRA: medical dictionary for regulatory activities

MMP: matrix metalloproteinase

NO: nitric oxyde

NOAEL: no observed adverse effect level

NRS: numerical rating scale

NSAID: nonsteroidal anti-inflammatory drug

OA: osteoarthritis

OARSI: osteoarthritis research society international PCSA: potentially clinically significant abnormality

PD: pharmacodynamic(s)
PGE2: prostaglandin 2
PK: pharmacokinetic(s)
PKA: protein kinase A
SAE: serious adverse event

SAE: serious adverse event SAP: statistical analysis plan

SC: subcutaneous(ly)
SD: standard deviation

Sox9: SRY-Box Transcription Factor 9

SUSAR: suspected unexpected serious adverse reaction

t1/2: elimination half-life

TEAE: treatment-emergent adverse event Tmax: time to maximum concentration

ULN: upper limit of normal

WOCBP: women of childbearing potential

### 1 Abbreviations

AE Adverse event

AESI Adverse event of special interest ALT Alanine aminotransferase

AST Aspartate aminotransferase
ATC Anatomical therapeutic chemical

AUC Area under the curve
CrCl Creatinine clearance
Cmax Maximum concentration

CRF Case report form
CSR Clinical study report
DLT Dose Limiting toxicity

DSMB Data and safety monitoring board

ECG Electrocardiogram

eCRF Electronic case report form EMA European medical agency

EoS End of Study FU Follow up

GLP-1(R) Glucagon-like peptide 1 (receptor)

ICF Informed consent form

ICH International council for harmonisation

IA Intra-articular

IMP Investigational medicinal product KL Kellgren and Lawrence classification

MedDRA Medical dictionary for regulatory activities

MTD Maximum tolerated dose NRS Numerical rating scale

NSAID Nonsteroidal anti-inflammatory drug

OA Osteoarthritis

OARSI Osteoarthritis research society international PCSA Potentially clinically significant abnormality

PΚ Pharmacokinetic(s) PT Preferred term PTE Pre-treatment event SAE Serious adverse event SAP Statistical analysis plan SAS Statistical analysis system Standard deviation SD SOC System organ class

SUSAR Suspected unexpected serious adverse reaction

T1/2 Elimination half-life

TEAE Treatment-emergent adverse event

TK Target Knee

Tmax Time to maximum concentration

ULN Upper limit of normal

### 2 Introduction

This Statistical Analysis Plan (SAP) describes the planned analysis and reporting for clinical research study LASARE "A Phase I Clinical Trial to Evaluate the Safety, Tolerability, and Pharmacokinetics of Single Ascending Doses of 4P004 Versus Placebo Injected in the Target Knee Joint of Patients with Grade 2 to 4 Osteoarthritis on the Kellgren and Lawrence Severity Index".

This study is being completed to characterize the safety and the tolerability of single IA administration of 4P004 at escalating doses (MTD) defined by occurrence of Dose Limiting Toxicities (DLTs).

The structure and content of this SAP provides sufficient detail to meet the requirements identified by the EMA and International Conference on Harmonization of Technical Requirements for Registration of Pharmaceuticals for Human Use (ICH): Guidance on Statistical Principles in Clinical Trials.

The following documents were reviewed in preparation of this SAP:

- Clinical Trial Protocol (4MB-LAS-P Version 3.0 July 2023)
- AdClin SOP "Clinical Data Analysis"
- ICH Guidance Topic E9 "Statistical Principles for Clinical Trials"
   [https://www.ema.europa.eu/en/documents/scientific-guideline/ich-e-9-statistical-principles-clinical-trials-step-5 en.pdf]

### 3 Purpose

The purpose of this SAP is to outline the planned analyses to be completed to support the completion of the Clinical Study Report (CSR) for the Clinical Trial Protocol 4MB-LAS-P, version 3.0 (17-07-2023), of the clinical research study LASARE "A Phase I Clinical Trial to Evaluate the Safety, Tolerability, and Pharmacokinetics of Single Ascending Doses of 4P004 Versus Placebo Injected in the Target Knee Joint of Patients with Grade 2 to 4 Osteoarthritis on the Kellgren and Lawrence Severity Index". The planned analyses identified in this SAP will be included in regulatory submissions and/or future manuscripts.

Of note, since the study is primarily designed for safety and tolerability, complementary analyses may be performed to support the clinical development program. Any analysis performed but not identified in this SAP will be clearly identified in the respective CSR.

### 4 Study Objectives

The primary objectives are

- To characterize safety and tolerability of single IA administration of 4P004 at escalating doses
   in participants with knee OA grade 2 to 4 osteoarthritis (OA) on the Kellgren and Lawrence severity index (KL 2-4).
- To determine the maximum tolerated dose (MTD) defined by occurrence of Dose Limiting Toxicities (DLTs) in participants with knee OA KL 2-4.

The secondary objective is

 To characterize the plasma pharmacokinetics (PK) of liraglutide when administered as single IA doses at escalating dose levels in participants with knee OA KL 2-4.

The exploratory objective is

To collect biological fluids (blood, urine)

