#### 8.5.2 Inclusion visit, D1, full day hospitalization

During this visit (24 hours hospitalization), the Investigator will:

- review inclusion / exclusion criteria, concomitant medication (from screening),
- do physical exams, ECGs, measure vital signs as per D1-D2 Study Flowchart (section 1.2.2),
- record any AE since screening,
- put a veinous line,
- remind the participant to fill in the NRS (before any study intervention on D1) for assessing target knee pain in the previous 2 days and during the hospitalization as outlined in section 1.2.2.
- randomize the participant (performed by the pharmacist)
- take blood / urine samples for glycemia, PK and OA-related biomarkers samples as per D1-D2 Study Flowchart (section 1.2.2),
- do the IA injection (modalities given in section 6.2.2 and in the Investigator manual) of the IMP extemporaneously prepared in a vial by the pharmacist (procedure for preparation is detailed in the Pharmacy manual).
- record AEs as per D1-D2 Study Flowchart (section 1.2.2),
- monitor the participant during the coming 24 hours:
  - o on local reaction as per D1-D2 Study Flowchart (section 1.2.2)
  - o on blood sugar level (veinous / capillary measures):
    - after IMP injection, glycemia will be systematically monitored (capillary measures via glucose meter and/or veinous measures) as per D1-D2 Study Flowchart (section 1.2.2),
    - when planned measurement indicates glycemia is ≤ 70 mg/dL without clinical symptom repeat the test each 30 min up to obtaining threshold value >70 mg/dL,
    - at any time if occurrence of one or more symptoms of hypoglycemia (common presenting symptoms include nausea, confusion, tremor, sweating, palpitations, or hunger), sugar will be given to the participant and a blood glycemia test should be immediately performed and closely monitored.

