#### 10 STATISTICAL METHODS

#### 10.1 Statistical and analytical plans

A statistical analysis plan (SAP) will be prepared and finalized prior to database lock. This document will provide further details regarding the definition of analysis variables and analysis methodology to address all study objectives.

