# Clinical safety laboratory evaluation

Individual results of laboratory tests from hematology, and chemistry that meet PCSA criteria to be defined in the SAP will be listed and summarized. Baseline, post-dose, and change from Baseline to post-dose laboratory data will be summarized. All clinical laboratory data will be listed.

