### **Table TTT. Chemistry over Time**

### **Table TTT. Chemistry PCSA over Time**

Glycemia is measured as follows:

Visit	Timepoint	Method
Screening	-	Blood
Visit 2	Pre-Dose	Blood & Glucometer
Visit 2	1h Post-Dose	Glucometer
Visit 2	2h Post-Dose	Blood
Visit 2	4h Post-Dose	Blood
Visit 2	6h Post-Dose	Glucometer
Visit 2	8h Post-Dose	Blood
Visit 2	10h Post-Dose	Glucometer
Visit 2	12h Post-Dose	Blood
Visit 2	16h Post-Dose	Blood
Visit 2	24h Post-Dose	Glucometer
Visit 3	-	Blood & Glucometer

In order to obtain one value per scheduled timepoint:

- The baseline value will be selected as the last measure before IMP injection. If there are such two measures (same time, different method), then Blood will be selected.
- Post-baseline, if there are two measures for a scheduled timepoint, Blood will be selected.
- Additional samples vs. scheduled samples will not be analyzed, unless they are the baseline.

The values will be reported over time (Baseline, 1h Post-Dose to 24h Post-Dose) with the same template as Vital Signs.

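### The DLT-based MTD is a primary objective, but the SAP plans no dedicated DLT count, DLT listing or MTD statement, and its glycemia table leaves out unscheduled post-dose lows

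*SAP*

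**What the plan says.** **Objective.** Protocol 3.1.1 and SAP 4 both name two primary objectives. The second is "To determine the maximum tolerated dose (MTD) defined by occurrence of Dose Limiting" Toxicities. Protocol 10.1 says of the SAP: "This document will provide further details regarding the definition of analysis variables and analysis methodology to address all study objectives".

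**DLT definition.** Protocol 4.6.1 bases DLT on expert opinion and any related SAE. It itemises anaphylaxis, blood glucose of 2.5 mmol/L or less within 2 days, amylase of 3 ULN or more within 7 days, and a serious gastrointestinal event within 7 days. More than 1 DLT in a cohort stops escalation, and that dose is called non-tolerated.

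**Glucose tests.** Protocol 8.5.2 adds tests to the schedule in two cases during the 24-hour stay. After a planned value of 70 mg/dL or less without symptoms, the site must "repeat the test each 30 min up to obtaining threshold value" above 70 mg/dL. If symptoms of hypoglycemia occur ("common presenting symptoms include nausea", among others), "sugar will be given to the participant and a blood glycemia test should be immediately performed and closely monitored".

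**Glucose analysis.** SAP 12.7 selects one value per scheduled timepoint and states: "Additional samples vs. scheduled samples will not be analyzed, unless they are the baseline". It continues: "The values will be reported over time (Baseline, 1h Post-Dose to 24h Post-Dose"), in the vital-signs layout, which includes PCSA rows. SAP 19 sets the glycemia PCSA at below 70 mg/dL. For laboratory tests in general, Protocol 10.1.4 says: "Individual results of laboratory tests from hematology, and chemistry that meet PCSA criteria to be defined in the SAP will be listed and summarized".

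**The concern.** The protocol leaves the analysis of every objective to the SAP. The SAP restates the MTD objective and then never returns to it. Unless this is fixed before lock, someone will have to decide after unblinding which events were DLTs, which samples count and what rule turns the count into an MTD. SAP 6.2 would place such unplanned work in CSR appendices, which is a poor home for a primary objective.

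The only MTD wording tied to trial data is in Protocol 2.3. There the sponsor's blinded review of cohort 3 says the MTD may have been reached, on nausea in 5 participants and vomiting in 4 of them. It cites no DLT.

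The glucose rule adds a second, narrower problem. The number and percentage of participants with a PCSA in glycemia is part of a primary endpoint (Protocol 3.2.1). Yet the samples most likely to catch a true low, those taken because the participant felt unwell, are the ones the table excludes.

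**Working it through.** **1. The plan's own figure.** 4 cohorts × (6 active + 2 placebo) = 32, which agrees with the synopsis. The sample size rests on no power calculation, so there is nothing further to reproduce.

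**2. Where DLT and MTD appear in the SAP.** They appear in section 1 (abbreviations), section 2 (introduction) and section 4 (objectives). They do not appear in sections 8 to 16, in the output list of section 17, in the listings of section 18 or in the PCSA table of section 19. The blacked-out text concerns dose levels. The output titles are legible, and none refers to DLTs or the MTD.

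**3. Each DLT criterion against the planned outputs.**

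| Criterion (Protocol 4.6.1) | Planned output that can show it | What is missing |
|---|---|---|
| Anaphylaxis | AESI tables by arm, AESI listing | DLT flag |
| Glucose ≤ 2.5 mmol/L, 2 days | Glycemia table (PCSA < 70 mg/dL); Listing 16.2.16; AESI outputs if reported as hypoglycemia | DLT limit; unscheduled samples in the table |
| Amylase ≥ 3 ULN, 7 days | Chemistry and chemistry PCSA tables (≥ 1.5 ULN); Listing 16.2.15 | DLT limit and window |
| Serious GI event, 7 days | SAE listing; SAE row of the TEAE overview | DLT flag |
| Any related SAE | SAE listing; SAE row of the TEAE overview | Count of related SAEs by dose |
| Expert opinion | None named | A place to record it |

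**4. Limits on one scale.** With the usual glucose factor of 18.016 mg/dL per mmol/L, 2.5 × 18.016 = 45.0 mg/dL, and 70 / 18.016 = 3.89 mmol/L. A value at the DLT limit is therefore also a PCSA, but the PCSA row cannot tell it from one just below 70 mg/dL. The same holds for amylase: every value of 3 ULN or more falls within the 1.5 ULN category and is not singled out.

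**5. What the additional-sample rule removes.** Scheduled post-dose glucose times are 1, 2, 4, 6, 8, 10, 12, 16 and 24 h, nine in all. The gaps from injection are 1, 1, 2, 2, 2, 2, 2, 4 and 8 h.

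- *Symptom-triggered test between scheduled times.* The low is excluded from the table. Sugar has been given, so the next scheduled value may be back above 70 mg/dL. The participant can then have no PCSA at any tabulated time.
- *30-minute repeats.* These follow a planned value of 70 mg/dL or less, which is itself in the table. The participant is already a PCSA case unless that value was exactly 70. What can be lost is the depth: a planned value between 45 and 70 mg/dL followed by a repeat at or below 45 mg/dL would be a DLT that the table does not show.

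**6. Why one event matters.** With 6 active participants, one DLT is 1/6 = 17% of the dose group, and the cohort rule turns on the step from 1 to 2. A missed event can change the conclusion for a dose.

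**7. From the count to an MTD.** The cohort rule in Protocol 4.6.1 names a non-tolerated dose. Neither document says how the MTD follows from it. Two features of this trial make a stated rule necessary. Cohort 4 tests an intermediate dose (Protocol 2.3), so cohort order is not dose order. Cohort 3 has an underdosed participant and a ninth enrolled (SAP 9.3), so counts by cohort and by actual dose may differ.

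**The case against.** The best defence is that most of the content is already there. Any hypoglycemia is an AESI, not only a severe one, and the AESI tables give participants and events by arm. Anaphylaxis is treated the same way, and serious events are listed. The glucose rule selects one value per timepoint for a by-time table, which is ordinary practice, and it removes nothing from Listing 16.2.16. The DSMB charter, which is not among the documents, may govern DLT review during escalation. SAP 3 allows complementary analyses.

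Much of this stands, and it limits the point. A reader might infer that the objective has no supporting output at all, or that DLT-level values vanish from the report. Neither follows: the components can be assembled by hand. It does not supply the count or the MTD statement, and DSMB advice during the trial is not a final analysis.

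Other stronger readings also fail:

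- No glucose is scheduled from 24 h until Visit 3, although the DLT window is 2 days, and the Visit 3 window can place the amylase sample after day 7. These are gaps in the protocol's sampling, which no SAP change can fill. Both extra-test triggers in Protocol 8.5.2 sit under the 24-hour monitoring.
- The 5 participants with nausea in cohort 3 do not measure how many tests were excluded. Onset times are not given, and the data are blinded and may include placebo.
- The nausea and vomiting judgement is not shown to lie outside the DLT concept, because Protocol 4.6.1 admits expert opinion.
- Protocol 10.1.4 does not say whether unscheduled samples enter the summaries, so the SAP is in tension with it rather than in plain breach.

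**Conclusion.** The point holds in this form. A primary objective has no dedicated DLT count, DLT listing or MTD statement, although the protocol says the SAP will cover all objectives. The gap begins in the protocol, whose primary endpoints (3.2.1) do not mention DLT or MTD either. The laboratory DLT criteria are not isolated at their own limits. The glycemia table and its PCSA rows can miss a low found only on symptoms, or understate the depth of one found on schedule.

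The size cannot be put as a number of participants, because the documents report no DLT data and no unscheduled glucose values. The individual data survive in listings, so the practical harm is limited to how a primary objective is answered and how completely one safety summary reads. This should be corrected before lock, but it does not threaten the trial's data. The conclusion assumes that the SAP as supplied is the full analysis plan and that no separate document prescribes the DLT analysis.

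**What to change.** Before database lock, amend the SAP in three places.

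1. **DLT table and listing.** Add one table of participants with a DLT by actual dose and one DLT listing by criterion. Apply Protocol 4.6.1 as written, including related SAEs and any expert-opinion DLT already documented.
2. **Glucose and amylase.** Keep the scheduled-time glycemia means as planned. Add two rows, the lowest post-dose value and any post-dose PCSA, using all post-dose samples. Take glucose and amylase DLTs from all samples within the 2-day and 7-day windows, and state how days are counted, since SAP 9.4 and the AE rule in Protocol 10.1.4 count 7 days differently.
3. **MTD statement.** Write down the rule, by dose level rather than cohort order. One example is the highest tested dose below any dose called non-tolerated under Protocol 4.6.1, or not reached if there is none. Note that the protocol itself defines only the non-tolerated dose. Report the cohort 3 nausea and vomiting judgement separately as a blinded sponsor decision, unless it was documented as an expert-opinion DLT.

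The cost is one table, one listing, two table rows and a short paragraph. It needs no new data and no change to the DLT definition. SAP 6.2 already bars database lock until the SAP is approved, so that approval is the natural point to add it.
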